12.2 Informed Consent Process

The principles of informed consent in the current edition of the Declaration of Helsinki will be implemented before any protocol-specified procedures or interventions are carried out. The screening consent form will describe the purpose of the study, the procedures to be followed, and the risks and benefits of participation. In the event of a female participant becoming pregnant, consent for follow-up of the pregnancy and outcome thereof will be requested.

Participants will be counselled about the available data regarding the efficacy of molnupiravir in preventing severe progression of COVID-19, and that there are only limited data from previous studies at this time.

Potential participants will have the opportunity to have any questions answered before and after signing the informed consent forms (ICFs). The informed consent process and all questions raised will be documented.

The study staff who conduct the informed consent process will also sign the ICFs. A copy of the consent form(s) will be given to the participant, and this fact will be documented in the participant's record.

Any participant who is rescreened should be reconsented and eligibility for the study must be rechecked prior to enrolment with regard to all other screening procedures.

12.3 Study Records and Confidentiality

The study site will establish a standard operating procedure for confidentiality protection. The site will ensure that study records including administrative documentation and regulatory documentation as well as documentation related to each participant enrolled in the study, including ICFs, locator forms, case report forms, notations of all contacts with the participant, and all other source documents are stored in a secure manner.

All laboratory specimens, evaluation forms, reports, and other records will be identified in a manner designed to maintain participant confidentiality. The exceptions are SARS-CoV-2 testing results, which are subject to local and national reporting. This may be name-based depending on local requirements. Local public health may contact participants diagnosed with SARS-CoV-2 for the purpose of surveillance and contact notification. Prior to SARS-CoV-2 testing, participants will be informed that results are reportable and may lead to contact by local public health officials if results are positive for infection.

All records will be kept in a secure storage area with limited access. Clinical information will not be released without the written permission of the participant, except as necessary for monitoring, and auditing by the Regulatory Authority or the IRB/EC(s).

The Principal Investigator or designee and all employees and co-workers involved with this study may not disclose or use, for any purpose other than performance of the study, any data, record, or other unpublished confidential information disclosed to those individuals for the purpose of the study.

All computers used during the study conduct will be password-protected, and records will only be accessible to authorised study staff.

12.4 Compensation for Injury

The Sponsor will ensure that compensation is provided for reasonable medical expenses incurred because of study-related injury, illness, or death, as determined according to the guidelines laid down by the Association of the British Pharmaceutical Industry (ABPI Compensation Guidelines Version 2014), and Guidelines for Good Practice in the Conduct of Clinical Trials in Human Participants in South Africa²⁴.

12.5 Participant Remuneration

For each day of protocol-related study procedures, the participants will receive compensation for travel costs to and from the clinic and inconvenience incurred, as per local regulating body recommendations.

13. ADMINISTRATIVE CONSIDERATIONS

13.1 Protocol Amendments

Any protocol amendments will be prepared by the Sponsor and submitted to the IRB/EC(s) and SAHPRA in accordance with local requirements.

Approval must be obtained from the IRB/EC(s) and SAHPRA (as required) before the implementation of any changes, except for changes necessary to eliminate an immediate hazard to participants, or changes that involve logistical or administrative aspects only (e.g., change in contact information).

13.2 Clinical Data Records

A log of names, signatures and initials of all staff authorised to enter data into a participant's clinic file and eCRF will be kept.

The Investigator will maintain paper or electronic source documentation for all study participants. Protocol-specific participant information will be captured in an eCRF. The Clinical Data Management System will comply with regulatory guidelines and requirements for electronic systems.

Data validation and quality control procedures will be detailed in the Data Management Plan.

All deviations from this study protocol will be documented in the Trial Master File and included in the final study report. An assessment of the significance of each protocol deviation will be presented in the clinical study report.

13.3 Record Retention

All source data, clinical records and laboratory data relating to the study will be archived for a minimum period after completion of the study in accordance with South African GCP guidelines, Sponsor and Funder requirements. Data will be available for retrospective review or audit by arrangement with the appropriate representative at the archiving organisation (e.g., Sponsor Head). Written agreement from [name] and BMGF, must precede destruction of the same.

13.4 Discontinuation of the Study

[name], the Sponsor, the Funder, the Principal Investigator, IRB/EC(s) and Regulatory Authority independently reserve the right to discontinue the study at any time for safety or other reasons. This will be done in consultation with the Funder, Sponsor and Principal Investigator where practical. In the event of premature termination or suspension of the study, the above-mentioned parties will be notified in writing by the terminator/suspender stating the reasons for early termination or suspension (with the exception of the Sponsor's responsibility for notifying the Regulatory Authority). Following such a decision, the Sponsor and the Investigator will ensure that adequate consideration is given to the protection of the participants' interest and safety. All ongoing participants will be followed up for a minimum of 28 days post initiation of the study drug and will be scheduled for an EOS visit. At this visit all assessments scheduled in accordance with the SOE (Section 1) will be performed (with the addition of safety laboratory samples if considered necessary due to safety considerations).

13.5 Publication Policy

A dissemination plan will be developed with all project partners prior to study completion. After study completion, results will be disseminated using the following strategies: written methods (i.e., publications in peer reviewed scientific journals), presentations at scientific conferences and workshops, in person dissemination of results to the research participants, and using electronic methods such as the project website and electronic media to publish results.

13.6 Study Audits

Audits may be carried out by the Sponsor quality assurance representatives, local authorities, or authorities to whom information on this study has been submitted. All documents pertinent to this study must be made available for such inspections after adequate notice of the intention to audit is provided.

APPENDIX 2: THE INFLUENZA PATIENT-REPORTED OUTCOME INSTRUMENT (FLU-PRO[®] Plus)

To be completed on D1-10, and D28:

FLU-PRO Plus[®]

People experience viral respiratory tract infections in different ways. We would like to know about the symptoms you have been experiencing during the past 24 hours. For each symptom, please mark one box under the response that best matches your experience. Mark the "Not at all" box, if you did not have that symptom in the past 24 hours.

What time is it? _____ AM / PM (please circle)

Please rate the extent to which you had each symptom during the past 24 hours.

	Not at all	A little bit	Somewhat	Quite a bit	Very much
Runny or dripping nose					
Congested or stuffy nose					
Sinus pressure					
Scratchy or itchy throat					
Sore or painful throat					
Difficulty swallowing					
Teary or watery eyes					
Sore or painful eyes					
Eyes sensitive to light					
Trouble breathing					
Chest congestion					
Chest tightness					
Dry or hacking cough					
Wet or loose cough					
Felt nauseous (feeling like you wanted to throw-up)					
Stomach ache					
Felt dizzy					
Head congestion					
Headache					

August 20, 2015 FLU-PRO Version 2.0

Research Tool in Development: Do NOT copy or distribute

Copyright © 2014- 2020 Leidos Biomedical Research, Inc. All Rights Reserved

Please rate the extent to which you had each symptom during the past 24 hours.

	Not at all	A little bit	Somewhat	Quite a bit	Very much
Lack of appetite					
Sleeping more than usual					
Body aches or pains					
Weak or tired					
Chills or shivering					
Felt cold					
Felt hot					
Sweating					

In the past 24 hours, how often have you had any of the following symptoms?

	Never	Rarely	Sometimes	Often	Always
Sneezing					
Coughing					
Coughed up mucus or phlegm					

	0 times	1 time	2 times	3 times	4 or more times
How many times did you vomit?					
How many times did you have diarrhea?					

In the past 24 hours, did you have any of the following symptoms?

	No	Yes
Loss of smell		
Loss of taste		

August 20, 2015 FLU-PRO Version 2.0

Research Tool in Development: Do NOT copy or distribute

Copyright © 2014- 2020 Leidos Biomedical Research, Inc. All Rights Reserved

APPENDIX 3: DAILY SURVEY

To be completed on D1-10, and D28

FLU-PRO® Plus GLOBAL ADDITIONAL DAILY DIARY ITEMS:

Copyright © 2014- 2020 Leidos Biomedical Research, Inc. All Rights Reserved

Items to be asked in daily diary through to Day 10, and on Day 28 along with the FLU-PRO® symptom items.

1. Overall, how severe were your infection symptoms today? (Please select one response only)

- 0 No flu symptoms today
- 1 Mild
- 2 Moderate
- 3 Severe
- 4 Very severe

2. Overall, how were your infection symptoms today compared to yesterday? (Please select one response only)

- 1 Much better
- 2 Somewhat better
- 3 A little better
- 4 About the same
- 5 A little worse
- 6 Somewhat worse
- 7 Much worse

3. How much did your infection symptoms interfere with your usual activities today? (Please select one response only)

- 1 Not at all
- 2 A little bit
- 3 Somewhat
- 4 Quite a bit

4. Have you returned to your usual activities today?

- 1 Yes
- 0 No

5. In general, how would you rate your physical health today? (Please select one response only)

5 Excellent
 4 Very Good
 3 Good
 2 Fair
 1 Poor

6. Have you returned to your usual health today?

1 Yes
 0 No
 5 Very much

GENERAL DAILY DIARY ITEMS:

1. Have you taken your daily medication as prescribed today?

Yes
 No
 Not applicable

2. Take your vitals: (time of day: _____ : _____ hh:mm)

- Pulse _____ beats per minute
- Temperature _____ °C
- Oxygen saturation level _____ %

3. Have you taken any other medications?

Yes
 No

If "yes", describe: _____

4. Have you observed any change or new complaint since you last completed the survey?

Yes
 No

If "yes", describe: _____

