
Objectives
 
 • To facilitate same-day COVID-19 diagnosis and treatment initiation in adults with mild COVID-19 and comorbid conditions • To assess the tolerability of molnupiravir in adults with mild COVID-19 • To describe time to symptom resolution in adults with mild COVID-19 treated with molnupiravir compared to placebo • To evaluate maximum COVID-19 disease severity in adults treated with molnupiravir compared to placebo • To evaluate the relationship between effectiveness of molnupiravir and time between onset of symptoms and initiation of treatment • To describe adherence to a 5-day course of molnupiravir in adults with mild COVID-19 • To evaluate the utilisation of health care services by adults with mild COVID-19 treated with molnupiravir compared to placebo 	
Endpoints
 
 • Proportion of enrolled patients for whom diagnosis and same day treatment initiation was facilitated through use of a LumiraDx™ rapid antigen test • Severity of adverse events • Adverse event-related study drug discontinuations • Time to sustained resolution of symptoms as reported in the Flu-PRO® Plus • Maximum score on the WHO Clinical Progression Scale from Day 1 to Day 29 • Number of days from symptom onset to initiation of treatment • Incidence of hospitalisation ((≥24 hours of care in a hospital or similar acute care facility) and/or death to Day 29 in patients with co-morbid conditions • Time to sustained resolution of symptoms as reported in the Flu-PRO® Plus • Maximum score on the WHO Clinical Progression Scale from Day 1 to Day 29 • Proportion of patients completing the course of molnupiravir as prescribed • Rate of hospital, emergency facility, clinic, health care practitioner or home visits to Day 29

To report the incidence and outcome of pregnancies in female participants who received molnupiravir	
Incidence of pregnancy in female participants to Day 2920-week gestational age ultrasound findingsPregnancy complicationsPregnancy outcomeInfant wellbeing to three months of age
Exploratory	
Objectives	

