6.1.5 IMP administration

Molnupiravir capsules can be taken with or without food. Each dose should be swallowed whole with fluid (e.g., a glass of water). The capsules should not be opened, crushed or chewed.

Participants will be provided with dosing instructions at the time of enrolment and when study drug is dispensed. They will self-administer the study treatment approximately 12-hourly for five days (10 consecutive doses).

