6.1.6 Treatment compliance

All participants will be asked to complete a daily survey to gather information regarding treatment compliance.

If the participant notices that they have missed a dose of molnupiravir within 10 hours of the time that it was scheduled, they should take the missed dose as soon as possible and resume the normal dosing schedule thereafter. If a participant misses a dose by more than 10 hours, they should not take the missed dose and instead take the next dose at the regularly scheduled time. The participant should not double the dose to make up for a missed dose.

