8.3 Efficacy Assessments

8.3.1 Patient Reported Outcomes

Participants will be asked to complete the following surveys during the study:

- The FLU-PRO[®] Plus questionnaire¹⁹⁻²¹ to assess the symptomatic extent of their illness (Appendix 2)
- The daily survey (Appendix 3) that includes:

- The FLU-PRO[®] Plus Global Additional Daily Diary Items (related to general well-being, overall severity of symptoms, and ability to perform usual daily activities)
- General daily diary items (related to study drug administration, recording of vital signs and SpO₂ measurements, review of concomitant medications, and information related to possible adverse events).

These surveys will be completed electronically or using a participant diary. Participants will be contacted via telephone call or text/direct messaging or web-based conference on day 3/6/10 by a staff member to confirm any AE occurrence, general well-being and update the WHO clinical progression scale. The participants will fill in the surveys daily themselves for 10 days, these will be collected at EOS or if electronically captured, before then.

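### The only diary item on compliance names no study drug and takes one answer for two daily doses, so the course-completion endpoint can be misstated in either direction

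*Protocol*

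**What the plan says.** Section 3 lists a secondary objective, "To describe adherence to a 5-day course of molnupiravir in adults with mild COVID-19", with the endpoint "Proportion of patients completing the course of molnupiravir as prescribed". Section 6.1.5 sets the course at two doses a day for five days, ten doses in all.

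Section 6.1.6 names one source of compliance data: "All participants will be asked to complete a daily survey to gather information regarding treatment compliance". It also gives a missed-dose rule: a dose missed by more than 10 hours is left out, and the next is taken at its usual time.

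The compliance item in Appendix 3 is "Have you taken your daily medication as prescribed today", with the answers Yes, No and Not applicable. The survey carries the instruction "To be completed on D1-10, and D28". A later item in the same list asks separately about other medicines. Section 8.3.1 describes this part of the survey as "General daily diary items (related to study drug administration, recording of vital signs" and further topics, and a footnote to the Schedule of Events says much the same.

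The Schedule of Events marks study treatment up to Day 5. It also schedules the return of unused drug and empty containers at the end-of-study visit, or from Day 6 if there is an earlier contact visit. Section 6.1.1 requires drug accountability records. Section 6.1.6 mentions neither returns nor records.

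**The concern.** The endpoint concerns a ten-dose course, but the instrument gives one categorical answer per day and does not say which medicine it means. There are two separate weaknesses.

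- **Which drug.** Under Section 5.1, participants can qualify through diabetes, hypertension, HIV or active TB, and Section 6.2.1 prohibits no concomitant treatment. For someone on long-term therapy, a question about daily medication can be taken to mean that therapy. The item is still asked on Days 6 to 10 and Day 28, after the course should be over, which may encourage that reading.
- **How many doses.** No answer records that one of two doses was taken. A participant who omitted a late dose, as Section 6.1.6 instructs, may honestly consider that they followed the prescription and answer Yes.

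Only the protocol is at hand. An analysis plan can define how completion is derived, but it cannot recover dose counts that the diary never asked for.

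**Working it through.** The protocol gives no figure for adherence, so there is none to reproduce. Its one design figure, 1863 per arm for 6% against 4% with 80% power, does reproduce (two-sided 5% assumed) but has no bearing here.

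**1. What an answer can mean on one treatment day**

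| Study doses taken | Item read as study drug | Item read as long-term therapy |
|---|---|---|
| Both | Yes | Yes, or No if a long-term medicine was missed: error downward |
| One of two | No, or Yes if the missed-dose rule was followed: error upward | Yes or No, unrelated to the study dose |
| Neither | No is the natural answer | Yes is possible: error upward |

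Errors can therefore run both ways. The protocol gives neither the expected mix of conditions nor the frequency of each reading.

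**2. Illustration of the upward error**

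Inputs: ten doses at two a day (Section 6.1.5). Three assumptions are not in the documents: each dose is taken with probability p, doses are independent, and a day with exactly one missed dose is answered Yes with probability s. A day with both doses missed is answered No.

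- True completion = p^10
- Reported completion = [p² + s·2p(1−p)]^5

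For p = 0.95: p² = 0.9025 and 2p(1−p) = 0.095.

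- True: 0.95^10 = 59.9%
- s = 0: 0.9025^5 = 59.9%
- s = 0.25: 0.92625^5 = 68.2%
- s = 0.5: 0.95^5 = 77.4%
- s = 1: 0.9975^5 = 98.8%

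| p | True | Reported, s = 0 | s = 0.5 | s = 1 |
|---|---|---|---|---|
| 0.95 | 59.9% | 59.9% | 77.4% | 98.8% |
| 0.98 | 81.7% | 81.7% | 90.4% | 99.8% |
| 0.99 | 90.4% | 90.4% | 95.1% | 100.0% |

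Over these values the overstatement runs from 0 to 39 percentage points (98.8 − 59.9 = 38.9). The downward error is not modelled, because nothing in the protocol suggests how often long-term medicines are missed.

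**3. Calendar**

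The tenth dose falls 9 × 12 = 108 hours after the first, which is four and a half days. A first dose after noon on Day 1 therefore puts the tenth on Day 6. In that case Day 1 holds one dose, Days 2 to 5 hold eight, and one remains. The Schedule of Events marks treatment only to Day 5. The diary itself runs to Day 10, so it would cover the last dose.

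**The case against.** The case against is substantial.

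- **The study drug is meant.** Section 8.3.1 and the Schedule footnote say so, and the separate item on other medicines points the same way. A reader might infer that the item measures the wrong drugs, but the text supports only that some participants may misread it. Those descriptions are protocol text and are not part of the item as participants see it, so the ambiguity remains.
- **A partial day can be answered.** The item is not strictly yes/no, and someone who missed one dose can answer No. It goes too far to say that such a participant has no correct answer. What stands is that Yes is also defensible for someone who followed the missed-dose rule.
- **Asking after Day 5 is not itself a fault.** Not applicable covers those days, and a late tenth dose needs Day 6.
- **The diary is not the only possible source.** Returns and accountability records allow a count, and completion does not require each missed dose to be dated. This stands. However, Section 6.1.6 does not link the count to the endpoint.
- **Chronic disease is not universal.** Age 65 or over qualifies alone, as does obesity or previous TB from age 50, and none of these implies daily medication. The protocol does not support saying that most participants take it.
- **The per-protocol set does not depend on this item.** A reader might infer that it needs dose-level exposure, but Section 10.2 defines it by completing the study without major deviations and gives no dose threshold.

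**Conclusion.** The point holds as a measurement weakness. The one compliance item fixed in the protocol neither identifies the study drug nor counts its doses, so course completion can be misclassified, and later analysis of the diary alone cannot repair that.

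The size is unknown. The range of 60% to 99% reported against 60% true rests on an assumed 5% missed-dose rate, independent doses and an assumed pattern of answering. Overstatement is zero if every day with a missed dose is answered No. A reader might conclude that completion will be overstated, but the documents do not support that certainty, because a missed long-term medicine answered No would pull the figure down.

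The endpoint is secondary and descriptive, and the primary comparison of hospitalisation and death is unaffected. The change is still worth making because it costs little. The Day 5 and Day 6 question depends on a late first dose and only needs the passages to be made consistent.

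**What to change.** - **Appendix 3:** replace the item with one that names the study capsules and asks how many doses of them were taken that day (0, 1 or 2), with a reason if a scheduled dose was missed. Ask it until all ten doses are accounted for as taken or missed. Judge completion on the total, since Day 1 may hold only one dose.
- **Section 6.1.6:** state that completion is derived from this diary, reconciled with the count of returned capsules, and say which source prevails if they disagree. At four 200 mg capsules per dose (Section 4.2), a course is 4 × 10 = 40 capsules. If a pack holds exactly one course, four returned capsules correspond to one missed dose.
- **Schedule of Events and Section 6.1.5:** reconcile treatment shown to Day 5 with ten consecutive 12-hourly doses when the first is taken late on Day 1.

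The cost is a slightly longer diary item, a short addition to Section 6.1.6 and a count of returns that are already collected. These are changes to measurement and wording only.

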APPENDIX 4: WHO ORDINAL SCALE FOR CLINICAL IMPROVEMENT

Patient State	Descriptor	Score
Uninfected	Uninfected; no viral RNA detected	0
Ambulatory	Asymptomatic; viral RNA detected	1
	Symptomatic; independent	2
	Symptomatic; assistance needed	3
Hospitalized: moderate disease	Hospitalized, no oxygen therapy*	4
	Hospitalized; oxygen by mask or nasal prongs	5
Hospitalized: severe disease	Hospitalized; oxygen by NIV or high flow	6
	Intubation and mechanical ventilation, $pO_2/FiO_2 \geq 150$ or $SpO_2/FiO_2 \geq 200$	7
	Mechanical ventilation, $pO_2/FiO_2 < 150$ ($SpO_2/FiO_2 < 200$) or vasopressors	8
	Mechanical ventilation $pO_2/FiO_2 < 150$ and vasopressors, dialysis, or ECMO	9
Dead	Dead	10

ECMO=extracorporeal membrane oxygenation; FiO₂=fraction of inspired oxygen; NIV=non-invasive ventilation; pO₂=partial pressure of oxygen; SpO₂=oxygen saturation

*If hospitalised for isolation only, record status as for ambulatory patient.

WHO Working Group on the Clinical Characterisation and Management of COVID-19 infection. A minimal common outcome measure set for COVID-19 clinical research. *Lancet Infect Dis.* 2020; 20: e192-e197
